3.7 CONTROL GROUPS

Mutation carriers who receive placebo treatment will comprise the primary control comparison group.

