4.10.4 Safety Analysis

The safety analysis population in Study Period A will consist of all carrier participants with at least one dose of study medication. The participants in this population will be grouped according to treatment received.

If the Sponsor decides to initiate an OLE study, safety data from Study Period B will also be used to contribute to the safety analysis in the OLE study. In this case, the safety analysis population in Study Period B will be grouped according to the treatment received in Study Period B. Safety assessments will be on the basis of adverse event reports, the results of vital signs, physical examinations, MRI evaluations, immunogenicity as measured by ADAs, and clinical laboratory tests.

Observed toxicities and adverse events will be coded and tabulated using the MedDRA; the frequencies of participants who receive active medication and those who receive placebo will be compared using descriptive statistics and reviewed for potential clinical significance and importance. Treatment-emergent adverse event tabulations will be provided overall, by severity, for serious adverse events, and further subcategorized by relationship to study drug.

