4. ANALYSIS SETS

The following analysis populations are defined for Study Period A:

Population	Definition
ITT	All randomized participants, whether or not the participant received the assigned treatment; participants are grouped according to the treatment assignment at randomization \times mutation status.
mITT	All randomized participants who received at least 1 dose of study drug; participants are grouped according to the treatment assignment at randomization; all primary and secondary efficacy analyses are based on the mITT population among the mutation carriers.
Safety-evaluable	All randomized participants who received at least 1 dose of study drug; participants are grouped according to the actual treatment received \times mutation status; mutation carriers randomized to placebo and mutation non-carriers randomized to placebo who received more than 2 doses of crenezumab will be grouped in the crenezumab arm; all participants who have received no more than 2 doses of crenezumab will be further grouped together in a placebo arm, regardless of the mutation status.
Pharmacokinetic-evaluable	All safety-evaluable participants with at least 1 plasma sample, provided sufficient dosing information (dose and dosing time) is available. Participants will be grouped according to the actual treatment received; participants randomized to placebo who received more than 2 doses of crenezumab will be grouped in the crenezumab arm.

Population	Definition
Tau-ITT	Tau substudy ITT population. All participants randomized in Study GN28352 and consented to the tau PET substudy, whether or not the participant received the assigned treatment; participants are grouped according to the treatment assignment at randomization \times mutation status.
Tau-mITT	Tau substudy modified ITT population. All participants randomized in Study GN28352 and consented to the tau PET substudy who received at least 1 dose of study drug; participants are grouped according to the treatment assignment at randomization; analyses on change in tau burden are based on Tau-mITT population among the mutation carriers.

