Tau-safety-evaluable	All participants randomized in Study GN28352 and consented to the tau PET substudy who received at least 1 dose of study drug; participants are grouped according to the actual treatment received \times mutation status; mutation carriers randomized to placebo and mutation non-carriers randomized to placebo who received more than 2 doses of crenezumab will be grouped in the crenezumab arm; all participants who have received no more than 2 doses of crenezumab will be further grouped together in a placebo arm, regardless of the mutation status.

ITT = intent-to-treat; mITT = modified intent-to-treat; PET = positron emission tomography.

5. **STATISTICAL ANALYSES**

5.1 **GENERAL CONSIDERATIONS**

Analyses for Study Period A includes the following:

- A primary analysis (*initial readout*) will occur after all participants have completed the Week 260 assessments
- *During Study Period B, safety analyses from Study Period A will be refreshed (due to the additional 16-week safety follow-up data accrued in Period A after the primary analysis) and reported in the final Clinical Study Report (CSR); no other analyses (e.g., primary and secondary endpoints and PK/PD endpoints) will be refreshed*

The analyses for Study Period B or the OLE study are described in Section 5.10.

All efficacy analyses will be performed on the modified intent-to-treat (mITT) population, unless otherwise specified. Participants will be analyzed according to the treatment assigned at randomization by IxRS.

All safety analyses will be performed in the safety-evaluable population, unless otherwise specified.

All data, including data collected after Week 260, will be used for the primary analysis.

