5.6.2 Adverse Events

All treatment-emergent adverse events, serious adverse events, adverse events leading to death, protocol-specified adverse events of special interest (including amyloid-related imaging abnormalities—edema/effusion [ARIA-E], amyloid-related imaging abnormalities— hemosiderin deposition [ARIA-H], cerebral macrohemorrhages, pneumonia, *potential drug-induced liver injury, and suspected transmission of infectious agents by the investigational product*) and adverse events leading to study treatment discontinuation will be summarized by MedDRA Preferred Term, appropriate thesaurus level by treatment arm. Adverse events will be summarized by severity and by relationship to study drug. For events of varying severity, the highest grade will be used in the summaries.

In addition, treatment-emergent injection reactions, infusion-related reactions and COVID-19 infections will be summarized by treatment group.

Only treatment-emergent adverse events will be included in the analyses, defined as any adverse event reported during or after the first dose of study drug. Adverse events with a missing onset date will be considered to be treatment-emergent. Adverse events with a partially missing onset date will also be included as treatment-emergent if the month (if it was recorded) and the year occur on or later than the month and year of the study treatment start date.

A separate listing of adverse events reported during the screening period (before the first dose of study drug) will also be produced.

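### The SAP defines both a split and a pooled placebo group for safety and does not name carrier placebo as the comparator; any contrast with the pooled arm mixes drug with mutation status

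*SAP*

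**What the plan says.** SAP Section 4 defines the safety-evaluable population in layers. The first is a split: "participants are grouped according to the actual treatment received \times mutation status". The next moves placebo-randomised participants, carriers and non-carriers alike, "who received more than 2 doses of crenezumab will be grouped in the crenezumab arm". The last is a pool: those with no more than 2 crenezumab doses "will be further grouped together in a placebo arm, regardless of the mutation status". The tau-safety-evaluable definition repeats all three.

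SAP 5.1 makes this population the default: "All safety analyses will be performed in the safety-evaluable population, unless otherwise specified". SAP 5.6.2 says that adverse events "will be summarized by MedDRA Preferred Term, appropriate thesaurus level by treatment arm". Sections 5.6.3 to 5.6.8 mostly say by treatment group. None of them says whether the placebo column is the split or the pooled one.

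The protocol points mainly to carriers. Its safety objective (Section 2.2, repeated in SAP Table 1) is crenezumab against placebo in mutation carriers. Section 3.7 states: "Mutation carriers who receive placebo treatment will comprise the primary control comparison group". Section 4.10.4 states: "The safety analysis population in Study Period A will consist of all carrier participants with at least one dose of study medication". Section 3.6, however, defines the safety-evaluable set as every randomised participant with at least one dose, without restriction to carriers.

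**The concern.** Non-carriers can be assigned only to placebo. The arm randomised to crenezumab is therefore all carriers, while the pooled placebo arm is a mixture of randomised carriers and non-carriers who were never eligible for the drug. A contrast between the two estimates the drug effect plus part of the carrier effect. If an event is less common in non-carriers, the pooled placebo rate falls below the rate in the proper control group, and crenezumab looks worse than it is. If it is more common, a real excess could be hidden.

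The documents give reason not to assume equal rates. Protocol 4.2 and SAP 1.2.3 say that non-carriers help to separate changes tied to the disease predisposition from those of normal ageing. Protocol 3.5.2 links ARIA to amyloid around blood vessels. ARIA-E and ARIA-H are events of special interest, so a distorted placebo rate would fall where the safety reading matters most. The comparison is descriptive, so no model adjustment would correct it.

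**Working it through.** **Which groups the text names.** The Section 4 definition uses the word arm for two groups only: crenezumab and the pooled placebo. SAP 5.6.2 then reports by arm. Elsewhere the SAP asks for a split explicitly: disposition (5.2) is by treatment group and mutation status, and study conduct and demographics (5.7.1, 5.7.2) present non-carriers as a group. Sections 5.6.2 to 5.6.8 have no such instruction, and 5.6.8 speaks only of crenezumab and placebo groups. The pooled reading is therefore the more natural one for adverse events, but the text does not settle it.

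**Inputs**
- Planned: about 100 participants in each of three arms (Protocol 3.1).
- Recruited: 252 in total (Protocol 3.2).
- Carriers: 84 + 84, from the simulation in SAP Appendix 2 that is set up to mimic this study.
- Non-carriers, inferred: 252 − 2 × 84 = 84.
- Event rates by carrier status: not in the documents. Assumed carrier rate p = 2%, 10% or 20%, with the non-carrier rate equal to r × p for r = 1, 0.5, 0.25 or 0.

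**Formula, with no drug effect.** The non-carrier share of the pooled arm is 84/168 = 0.5, or 100/200 = 0.5 as planned. The pooled placebo rate is (84p + 84rp)/168 = p(1 + r)/2. The crenezumab rate is p. Hence:
- apparent risk ratio = 2/(1 + r)
- apparent risk difference = p(1 − r)/2

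| Non-carrier rate relative to carriers (r) | Apparent risk ratio | Spurious difference, p = 2% | p = 10% | p = 20% |
|---|---|---|---|---|
| 1 | 1.00 | 0 | 0 | 0 |
| 0.5 | 1.33 | 0.5 points | 2.5 points | 5 points |
| 0.25 | 1.60 | 0.75 points | 3.75 points | 7.5 points |
| 0 | 2.00 | 1 point | 5 points | 10 points |

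The same calculation for crenezumab carriers against placebo carriers gives a ratio of 1 and a difference of 0 in every cell.

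**Precision given up by using carriers only.** With a common event rate, the standard error of the risk difference is proportional to √(1/84 + 1/84) = 0.154 for carriers only and √(1/84 + 1/168) = 0.134 for the pooled arm. The ratio is 1.15. The standard error of the placebo rate alone rises by √(168/84) = 1.41.

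**The case against.** The strongest reply is that the definition begins with the split by treatment and mutation status, and that pooling is described as a further step. This stands. Placebo carriers and placebo non-carriers exist as separate groups in the SAP. A reader might infer that the randomised carrier comparison has been removed, or that the trial's safety comparison as a whole is confounded; the text does not support either. It leaves the choice of comparator open.

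Other parts of the reply also stand:
- The protocol is not consistent with itself. The SAP population matches Protocol 3.6 and differs from 4.10.4, and naming a primary control group in 3.7 does not forbid an additional pooled one.
- The size is assumed. Participants entered without MCI or dementia, and those with more than 4 microhemorrhages, any superficial siderosis or any ARIA-E at baseline were excluded. Protocol 3.2.2 reports that about half of carriers were amyloid-PET negative at baseline. ARIA-E was seen in only 5 patients across all crenezumab studies as of December 2019 (Protocol 1.2.2.1), so rates of 10% to 20% do not describe it.
- Expected AD progression is not a good example of the bias, because Protocol 5.3.1.7 keeps it out of adverse event reporting unless there is doubt, the course is unexpected or treatment is suspected.
- A non-carrier with more than 2 crenezumab doses would be a dosing error, and nothing suggests that there are many.

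The reply does not remove the central point. The plan states a pooling rule, reports by arm, and nowhere says that carrier placebo is the safety comparator.

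**Conclusion.** The concern holds as a matter of specification, with a conditional bias. The SAP should not leave open whether crenezumab is set against placebo carriers or against a placebo arm that is about half non-carriers, because the second contrast departs from the safety objective, Protocol 3.7 and Protocol 4.10.4.

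The distortion is zero if event rates do not depend on carrier status. It reaches an apparent risk ratio of at most 2.00 if non-carriers have no events and the two placebo groups are of equal size. Intermediate values are illustrations. They rest on an inferred 84 non-carriers and on assumed rates, so a reader should not take them as a forecast of an excess in this trial.

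The difference from Protocol 4.10.4 is also undeclared: SAP Appendix 1 lists two changes, to the Period B safety population and to the reporting of adverse events in the 16-week follow-up, and not this one. That appendix is written against Protocol Version 10, whereas the protocol at hand is Version 11, so it needs updating in any case.

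**What to change.** - In SAP Section 4 (both safety-evaluable definitions) and at the start of Section 5.6, state that the main safety comparison is crenezumab carriers against placebo carriers.
- Show placebo non-carriers in their own column. If a pooled placebo column is kept, label it supplementary.
- List any non-carrier who received crenezumab separately, outside the crenezumab carrier column.
- Reconcile the SAP population with Protocol 3.6 and 4.10.4, which differ from each other, and record the outcome in SAP Appendix 1.

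This needs SAP wording and a column definition in the safety tables, and no new data. The downside is precision: the main comparator has about 84 participants instead of about 168, and the standard error of the risk difference is about 15% larger. A supplementary pooled column keeps the larger denominator in view for rare events.

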5.2 PARTICIPANT DISPOSITION

The analysis of participant disposition will be based on the intent-to-treat (ITT) population. Reasons for early discontinuation of treatment or early termination from the study will be listed and summarized by treatment group X mutation status.

5.3 PRIMARY ENDPOINTS ANALYSIS

The primary endpoint analysis from Study Period A will be based on the mITT population. The analysis will be adjusted by the factors used in randomization: age, education, apolipoprotein E (APOE) 4 carrier status (carrier vs. non-carrier), and baseline CDR zero versus CDR non-zero. The stratification factors as recorded in IxRS (see protocol for details) will be used.

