3.2.2 Rationale for Crenezumab Dosage

In this Phase II study, crenezumab 720 mg SC Q2W was selected as the dose and dosing regimen, following the results of the Phase II studies in sporadic AD; this dose provides similar exposures as the 15 mg/kg IV Q4W dose in Phase II that suggested a trend for efficacy in sporadic AD dementia. This SC dose has been administered in this study since August 2015 and has so far been well-tolerated. Since July 2019, a higher dose of 60 mg/kg IV Q4W is being offered to study participants as this is assumed to have a higher potential for efficacy and was also being investigated in Phase III studies in sporadic AD.

The Phase III studies (BN29552 [CREAD] and BN29553 [CREAD 2]) in patients with prodromal or mild (sporadic) AD tested a 4-fold higher dose (i.e., 60 mg/kg IV Q4W) of crenezumab than in Phase II compared with placebo. Based on results from a preplanned interim analysis of Study BN29552 assessing the safety and efficacy of crenezumab indicating that Study BN29552 was unlikely to meet its primary endpoint of change from baseline in CDR-SOB score, both Phase III studies were discontinued.

Study GN28352 continues given that this at-risk ADAD population differs from the sporadic prodromal to mild AD population in the following ways: the population is much younger, clinically asymptomatic at study entry, and carries a mutation that is specifically linked to amyloid metabolism. Approximately half of the carrier participants have been reported to have negative amyloid PET scans at baseline (Reiman et al. 2018). In addition, this *PSEN1 E280A* mutation is reported to be associated with an increased rate of amyloid accumulation in brain, as measured by amyloid PET compared with sporadic AD (Fleisher et al. 2015), suggesting the potential for crenezumab in delaying the progression of amyloid pathology may provide greater benefit in this patient population compared with sporadic AD. Furthermore, a quantitative systems pharmacology model of AD has been developed by Genentech and calibrated to both the ADAD (*PSEN1 E280A* mutation) and sporadic AD populations. Simulations from this model predict that both the 720 mg SC Q2W and 60 mg/kg IV crenezumab Q4W dosing regimens will delay the progression of amyloid

accumulation in the brain in the ADAD population, as measured by amyloid PET standard uptake ratio, with a greater effect associated with the 60 mg/kg IV Q4W regimen (internal data).

[figure not shown]

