4.10.3.1 Primary Efficacy Endpoints

The primary efficacy analysis will be performed on the mITT population. The primary endpoint family, 1) annualized rate of change on the API ADAD Composite Cognitive Test Battery total score and 2) annualized rate of change on the FCSRT Cueing Index, will be assessed using a mixed effects (ME) model. The model will be used to test the treatment effect on annualized rate of change adjusting for selected baseline characteristics and randomization factors. Statistical tests for the primary endpoints will be two-sided and performed at an overall 0.05 level: $\alpha=0.04$ for testing the treatment effect on the annualized rate of change on the API ADAD Composite Cognitive Test Battery total score; $\alpha=0.01$ for testing the treatment effect on the annualized rate of change on the FCSRT Cueing Index. Estimated treatment effects and CIs will also be provided as an aid to interpretation of study results.

In order to maximize the power, data beyond each participant's Week 260 assessment through the unblinding of the study will be included in the primary analysis or its sensitivity analysis.

All details of the prespecified statistical analyses for the primary efficacy endpoints will be provided in the SAP.

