5.3.3 Main Analytical Approach for Primary Endpoint Family

The primary analysis on both primary endpoints will be performed using a RCRM (Richeldi et al. 2014; Flaherty et al. 2019; Hu et al. 2021) with a missing at random (MAR) assumption. This model will include all observations, including baseline scores as the response variable. The RCRM will include the randomization stratification factors described in Section 5.3 as fixed effects with an intercept, and will include the categorical treatment groups as interaction terms with time; *stratification factor(s) may be removed from the model if there is risk of non-convergence or sparse strata (in case*

of non-convergence, stratification factors will be removed in the order of the smallest number of observations in any cell caused by that stratification factor).

Participant-level random intercept and random slope are also included in the model, where an unstructured covariance between the random intercept and random slope is assumed. The RCRM is constructed as follows:

$$Y_{ij} = \alpha + (\text{Randomization Factors})_i + u_{0i} + (\beta + \beta_x l_{x,i} + u_{1i}) t_{ij} + \varepsilon_{ij}$$

where Y_{ij} is the score for participant i at visit j ; t_{ij} is the duration in the unit of year after first drug intake for participant i at visit j ; $l_{x,i} = 1$ if participant i in a *PSEN1* E280A mutation carrier is in the crenezumab mITT group, and $l_{x,i} = 0$ if participant i is a *PSEN1* E280A mutation carrier is in the placebo mITT group; u_{0i} and u_{1i} are random intercept and random slope, respectively, for the i^{th} participant; ε_{ij} is the random error for the i^{th} participant at visit j . The crenezumab treatment effect on the rate of change is quantified by β_x ; the 95% CI and p-value for crenezumab treatment effect will be presented. The crenezumab treatment effect compared with the placebo group on the relative reduction (RR) scale is calculated as $-\beta_x/\beta \times 100\%$; its estimate will also be presented; its 95% CI using bootstrap approach will also be provided.

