5.3.5.1 Subgroup Analyses for Primary Endpoints

The following subgroups will be analyzed with respect to the primary endpoints using the same primary analysis. Forest plots will be presented to summarize the results.

The subgroup categories may be combined if there is not enough representation of a specific subpopulation or if the statistical model fails to converge.

- Age (≤ 38 vs. > 38)
- Education (< 9 years vs. ≥ 9 years)
- APOE4 carrier status (carrier vs. non-carrier)
- Baseline CDR zero vs. CDR non-zero
- Amyloid status at baseline (amyloid positive vs. amyloid negative) using a standardized uptake value ratio (SUVr) threshold (*details of the threshold will be prespecified in the biomarker analysis plan*)

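### The primary slope model leaves out baseline amyloid, a measurement already scheduled at screening, and so may forgo precision; adding it with a time interaction before unblinding is a cheap improvement.

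*SAP*

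**What the plan says.** **Protocol.** Section 4.10.3.1 describes a mixed model that tests the treatment effect on annualized change while "adjusting for selected baseline characteristics and randomization factors". It names no characteristic and hands over the specification: "All details of the prespecified statistical analyses for the primary efficacy endpoints will be provided in the SAP". Section 3.2.2 says: "Approximately half of the carrier participants have been reported to have negative amyloid PET scans at baseline". Appendix 1 schedules a florbetapir scan at screening, and its footnotes say that eligibility does not depend on the result. Section 3.8 stratifies randomization by age, education, APOE ε4 status and baseline CDR, not by amyloid.

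**SAP.** Section 5.3 restricts adjustment to the randomization factors: "The analysis will be adjusted by the factors used in randomization", which it lists as age, education, APOE4 status and baseline CDR. Section 5.3.3 places them on the level: "The RCRM will include the randomization stratification factors described in Section 5.3 as fixed effects with an intercept". On the slope, the model "will include the categorical treatment groups as interaction terms with time", and its equation multiplies time by nothing else except the participant's random slope. In the planned analyses of the primary endpoints, amyloid appears only as a subgroup in Section 5.3.5.1: "Amyloid status at baseline (amyloid positive vs. amyloid negative) using a standardized uptake value ratio (SUVr) threshold".

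SAP Section 1 says that the SAP supersedes the protocol's analysis plan. SAP Appendix 1 lists two changes from Protocol Version 10. Neither concerns covariates.

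**The concern.** The primary parameter, beta_x, is a difference in slopes. Its standard error depends on how much participants differ in their rate of decline. If carriers with and without amyloid at entry decline at different rates, that difference sits in the unexplained slope variance, and a baseline covariate could remove part of it.

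The issue is worth raising here because precision is tight. Protocol 3.2 reports 252 participants recruited against 300 planned, and the composite is now tested at 0.04 instead of 0.05. Protocol 4.10.8 itself records worries about the composite's sensitivity to change.

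There is a secondary issue. Amyloid is not a stratification factor, so the arms may differ by chance in the share of amyloid-positive carriers. The current model would leave the realised estimate unadjusted for that.

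**Working it through.** **1. The plan's own figure.** Inputs from SAP Section 3: 100 per arm, 25% dropout (so 75 completers), CV 0.65, a 30% reduction, two-sided 0.05, t-test.
- Noncentrality = 0.30 / (0.65 × √(2/75)) = 2.83.
- Power = 80.2%, against at least 80% stated. It reproduces, and it comes from an unadjusted t-test.

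**2. Present position, same approximation.** SAP Appendix 2 uses 84 per arm to mimic this study. With the plan's 25% dropout, 84 × 0.75 = 63 completers. The composite's alpha is 0.04 (SAP Section 2).
- Noncentrality = 0.30 / (0.65 × √(2/63)) = 2.59.
- Power = 69.7%.

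**3. Effect of explaining variance.** Let R² be the share of the variance in five-year change explained by baseline amyloid. This is an assumption; neither document gives it. The effective CV is 0.65 × √(1 − R²).

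| R² | Effective CV | Power (63 per arm, alpha 0.04) |
|---|---|---|
| 0% | 0.650 | 70% |
| 2% | 0.643 | 71% |
| 5% | 0.634 | 72% |
| 10% | 0.617 | 74% |
| 20% | 0.581 | 79% |
| 30% | 0.544 | 85% |

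No CV is stated for the FCSRT Cueing Index, so no corresponding figure can be drawn from the documents.

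**4. Main effect or time interaction.** A simulation used a random intercept and slope per participant, 75 per arm, alpha 0.05 and 4,000 runs per scenario. It assumed that amyloid explains 10% of intercept variance and set the intercept-slope correlation to 0.

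| R² on slope | No amyloid | Main effect only | Amyloid and amyloid-by-time |
|---|---|---|---|
| 10% | 0.802 | 0.800 | 0.835 |
| 20% | 0.817 | 0.810 | 0.879 |

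With correlation 0.3 and R² 20%, the three figures are 0.874, 0.857 and 0.916. Entering amyloid the way the SAP enters its other covariates gains nothing for the slope. All of the gain comes from the time interaction.

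**5. Chance imbalance.** With half of carriers positive, 84 per arm and simple randomization, the SD of the arm difference in positive share is √(2 × 0.25/84) = 0.077, or 7.7 points. The probability of a difference of at least 10 points is then 0.195. These are upper figures, because any balancing of amyloid through the stratification factors reduces them.

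In units of mean placebo decline, positives and negatives differ by 2 × 0.65 × √R². A 10-point imbalance shifts the estimate by one tenth of that:
- R² 5%: 0.10 × 0.291 = 0.029, or 10% of the assumed 0.30 effect.
- R² 30%: 0.10 × 0.712 = 0.071, or 24% of it.

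The standard error of the unadjusted comparison is 0.65 × √(2/84) = 0.100, so either shift is smaller than one standard error.

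**6. Type I error.** Under no treatment effect (intercept-slope correlation 0.3, R² 10% to 30%), the simulated error of the model without amyloid was 0.051 to 0.053.

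**The case against.** Three stronger readings are tempting, and the documents support none of them.

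- **A promise about amyloid was broken.** A reader might infer this from Protocol 4.10.3.1. That section names no variable and defers to the SAP, which takes precedence. The examples of baseline characteristics in Protocol 4.10.2 do not include amyloid. What stands is narrower: the SAP selects nothing beyond the randomization factors and does not list this in Appendix 1. That appendix is written against Protocol Version 10, and the protocol in hand is Version 11.
- **Power has been lost.** The 80% was computed without covariates and reproduces without them. The 70% above is a completers-only t-test, not the power of the planned model, which uses all observations, including those after Week 260. R² could also be near zero. Neither document links baseline amyloid to cognitive slope, and a composite with learning effects and measurement noise may leave little for amyloid to explain.
- **The estimate is biased.** Chance imbalance under randomization is covered by the standard error, and type I error holds. Nor is amyloid wholly unbalanced by design. Protocol 3.2.3 places the start of amyloid accumulation at around age 30, so stratifying by age may balance it in part.

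Two further points are fair. The amyloid subgroup analysis estimates treatment effects within each stratum, so amyloid is not ignored; but it does not give an adjusted primary estimate. Age-by-time or CDR-by-time terms might capture part of the same gain. In the current model those factors act only on the level, so they do not capture it now.

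**Conclusion.** The point holds as a cheap improvement, not as the correction of an error. A plausible baseline predictor of decline, scheduled for all participants before treatment, is absent from the primary model, and no baseline factor acts on the slope. In the approximation above, including it is worth nothing at R² 0%, about 2 points of power at 5%, 5 at 10%, 10 at 20% and 15 at 30%. These figures rest on CV 0.65, 63 completers per arm, alpha 0.04, a 30% effect and an R² that the documents do not supply. The chance difference in amyloid-positive share has an SD of at most about 7.7 points. If a sizeable difference occurred, the current model would not adjust the estimate for it. The unlisted handling of the protocol's covariate wording is a documentation gap only.

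**What to change.** Before unblinding:

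1. Add baseline florbetapir SUVr (continuous, centred at the pooled mean) and SUVr-by-time to the primary model for both primary endpoints. The time interaction is essential. Add no treatment-by-SUVr-by-time term, so that beta_x remains the single slope difference. Centring keeps the placebo slope in the relative-reduction formula of SAP 5.3.3 at average amyloid.
2. Set missing baseline SUVr to the pooled mean. The flowchart shows that scans were scheduled, not that all were obtained.
3. Keep the current model as a sensitivity analysis.
4. State in SAP Appendix 1 which baseline characteristics were selected under Protocol 4.10.3.1.

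The cost is SAP wording, two parameters per endpoint and a missing-scan rule. No new data collection is needed. If amyloid is only weakly related to slope, there will be little or no gain. If the sponsor prefers to leave the primary model alone, the minimum is to prespecify the amyloid-by-time model as a sensitivity analysis and to make the Appendix 1 entry.
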